2 STUDY OBJECTIVES AND ENDPOINTS

This is a Phase 2a, Multi-Center, Open-Label Study to Evaluate the Safety, Efficacy, and Pharmacokinetics of PRA023 in Subjects with Moderately to Severely Active Crohn’s Disease. The primary, secondary and exploratory study objectives and corresponding endpoints for IP analyses are listed in **Table 1** below.

Table 1 Study Objectives and Endpoints

Objectives	Endpoints
Primary	
To evaluate the safety and tolerability of PRA023 following 12-weeks of induction therapy	
 Proportion of subjects reporting AEs, SAEs, AEs leading to discontinuation, and markedly abnormal laboratory values
To assess the proportion of subjects with endoscopic improvement (decrease in simple endoscopy score for Crohn’s disease [SES-CD] \geq 50% from Baseline) at Week 12	
 Proportion of subjects with endoscopic improvement , as defined by decrease in SES-CD \geq 50% from Baseline at Week 12
Secondary	
To assess the proportion of subjects with clinical remission (Crohn’s disease activity index [CDAI] < 150) at Week 12	
 Proportion of subjects in clinical remission (CDAI < 150) at Week 12
To assess the proportion of subjects with endoscopy and clinical improvement at Week 12	
 Proportion of subjects with endoscopic and clinical improvement, as defined by decrease in SES-CD \geq 50% AND reduction in CDAI \geq 100 points from Baseline or CDAI <150 at Week 12
To assess the proportion of subjects with biomarker and clinical improvement, among subjects with at least one elevated biomarker at Baseline, at Week 12	
 Proportion of subjects with both biomarker and clinical improvement (decrease in hsCRP OR fecal calprotectin \geq 50% from Baseline, among subjects with at least one elevated biomarker at Baseline, AND reduction in CDAI \geq 100 points from Baseline or CDAI <150) at Week 12

To assess the proportion of subjects with normalization of C-reactive protein (hsCRP < upper limit of normal [ULN]), among subjects with elevated concentrations at Baseline, at Week 12	
 Proportion of subjects with normalization of hsCRP (as defined by hsCRP < ULN), among subjects with elevated concentrations at Baseline, at Week 12
To assess the proportion of subjects with normalization of fecal calprotectin (fecal calprotectin < ULN), among subjects with elevated concentrations at Baseline, at Week 12	
 Proportion of subjects with normalization of fecal calprotectin (as defined by fecal calprotectin < ULN), among subjects with elevated concentrations at Baseline, at Week 12
To assess the proportion of subjects with clinical improvement at Week 12	
 Proportion of subjects in clinical response, as defined by reduction in CDAI \geq 100 points from Baseline or CDAI < 150 at Week 12
To assess the proportion of subjects with two component patient-reported outcome (PRO-2) remission at Week 12	
 Proportion of subjects with PRO-2 remission (defined as average daily abdominal pain score \leq 1 point and average daily stool frequency \leq 3 points with abdominal pain and stool frequency no worse than Baseline) at Week 12
To assess the change in SES-CD score from Baseline to Week 12	
 Change in mean SES-CD score at Week 12 from Baseline
To assess the pharmacokinetics (PK) of PRA023	
 Descriptive summaries of PK and immunogenicity of PRA023
To assess the immunogenicity of PRA023	
 Proportion of subjects developing anti-drug antibody (ADA) and neutralizing antibody (Nab)
Exploratory	
To assess endoscopic remission at Week 12	
 Proportion of subjects with endoscopic remission, as defined as SES-CD \leq 4 and at least 2-point reduction from baseline and all individual score \leq 1 at Week 12
To assess ulcer-free at Week 12	
 Proportion of subjects with SES-CD ulcerated surface score of 0 at week 12 among patients with SES-CD ulcerated surface score \geq 1 at baseline
To assess the change in SES-CD segment score from baseline to Week 12	
 Change from baseline in SES-CD for each segment at Week 12
To assess the clinical improvement by PRO-2 score at Week 12	
 Change in PRO-2 over time Proportion of subjects with clinical improvement by PRO-2 score, defined as \geq 30% reduction of either score and no worsening in both scores at Week 12 Proportion of subjects with enhanced clinical response by PRO-2 score, defined as a reduction of \geq 60% in average daily stool frequency or a reduction of \geq 35% in average daily abdominal pain score, and no worsening in both scores at Week 12 Proportion of subjects with \geq 30% reduction of PRO-2 total score
To assess the proportion of subjects with both clinical improvement and endoscopic improvement at Week 12	
 Proportion of subjects who achieve both enhanced clinical response by PRO-2 score and endoscopic improvement at Week 12
To assess the IBDQ remission or IBDQ improvement at Week 12	
 Proportion of subjects with IBDQ remission or IBDQ improvement at Week 12
To assess the change from baseline in IBDQ scores at Week 12	
 Change from baseline in IBDQ scores
To assess the change in CDAI and component scores over time	
 Change in CDAI and components from Baseline over time

To assess the effects of PRA023 on tissue and serum pharmacodynamic (PD) markers, including tumor necrosis factor-like cytokine 1A (TL1A) concentrations, fecal calprotectin, and hsCRP in all subjects over time	
 • Change in PD markers including TL1A concentrations, fecal calprotectin, and hsCRP over time
To characterize the change in Perianal Disease Activity Index (PDAI) score from Baseline to Week 12	
 • Change in PDAI from Baseline over time
To characterize the effect of PRA023 for improvement and remission of enterocutaneous and/or perianal fistula -Overtime	
 • Proportion of subjects with improvement or remission of enterocutaneous and/or perianal fistula Overtime , among patients with fistula at baseline
To assess the change in global histological activity score (GHAS) and Roberts histopathology index (RHI) from Baseline to Week 12	
 • Change in mean GHAS and RHI scores from Baseline to Week 12 • Proportion of subjects with GHAS histologic score ≤ 4 at Week 12 • Proportion of subjects with Roberts histologic score < 5 at Week 12
To assess the proportion of subjects with histologic response and histologic remission at Week 12	
 • Proportion of subjects with GHAS histologic remission, defined as no neutrophils in the epithelium or subscore of 0, at Week 12 • Proportion of subjects with Roberts histologic remission (< 3) at Week 12

[figure not shown]

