#### 3.2 Secondary Endpoints

- The proportion of subjects in clinical remission (CDAI < 150) at Week 12
- The proportion of subjects with endoscopic and clinical improvement, as defined by decrease in SESCD  $\geq 50\%$  AND reduction in CDAI  $\geq 100$  points from Baseline at Week 12
- The proportion of subjects with both biomarker and clinical improvement (decrease in hsCRP OR fecal calprotectin  $\geq 50\%$  from Baseline, among subjects with at least one elevated biomarker at Baseline, AND reduction in CDAI  $\geq 100$  points from Baseline) at Week 12
- The proportion of subjects with normalization of hsCRP (as defined by hsCRP < ULN), among subjects with elevated concentrations at Baseline, at Week 12
- The proportion of subjects with normalization of fecal calprotectin (as defined by fecal calprotectin < ULN), among subjects with elevated concentrations at Baseline, at Week 12
- The proportion of subjects in clinical response, as defined by reduction in CDAI  $\geq 100$  points from Baseline at Week 12
- The proportion of subjects with PRO-2 remission (defined as average daily abdominal pain score  $\leq 1$  point and average daily stool frequency  $\leq 3$  points with abdominal pain and stool frequency no worse than Baseline) at Week 12
- Change in SES-CD score at Week 12 from Baseline
- Descriptive summaries of PK and immunogenicity of PRA023
- Proportion of subjects developing anti-drug antibody (ADA) and neutralizing antibody (Nab)

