### **6.4 Efficacy Assessment Description**

The SES-CD will be used to evaluate disease activity for the primary endpoint. The SES-CD and CDAI scores will be used to evaluate disease activity for the secondary endpoints. The SES-CD is a validated endoscopic score that is used to describe ileocolonoscopy findings in CD. SES-CD assesses the size of mucosal ulcers, the ulcerative surface, the endoscopic extension, and the presence of stenosis ([Daperno 2004](#), [Moskovitz 2007](#)).

For the current study, the following definitions will apply:

- Endoscopic Improvement – a decrease in SES-CD of  $\geq 50\%$  from Baseline
- Clinical Remission – CDAI  $< 150$
- Clinical Response – a reduction in CDAI  $\geq 100$  points from Baseline
- Biomarker and Clinical Composite Improvement – a decrease in hsCRP or fecal calprotectin  $\geq 50\%$  from Baseline and reduction in CDAI  $\geq 100$  points from Baseline

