- SAS® Software Version 9.4 (SAS Institute Inc., Cary, NC, USA.) is to be used for all analyses including tables, listings, and figures.
- Non-pharmacokinetic and non-biomarker lab data that are continuous in nature but are less than the lower limit of quantitation (LOQ) or above the upper LOQ will be imputed as follows:
 - A value that is 1 unit less than the LOQ will be used for calculation of descriptive statistics if the datum is reported in the form of “< x” (where x is considered the LOQ). For example, if the values are reported as < 50 and < 5.0, values of 49 and 4.9, respectively, will be used for calculation of summary statistics. An exception to this rule is any value reported as < 1 or < 0.1, etc. For values reported as < 1 or < 0.1, a value of 0.9 or 0.09, respectively, will be used for calculation of summary statistics.
 - A value that is 1 unit above the LOQ will be used for calculation of descriptive statistics if the datum is reported in the form of “> x” (where x is considered the LOQ). Values with decimal points will follow the same logic as above. The LOQ will be used for calculation of descriptive statistics if the datum is reported in the form of “≤ x” or “≥ x” (where x is considered the LOQ).
- PK plasma concentration values that are below the limit of quantitation (BLQ) will be treated as 0. PD/biomarker BLQ concentration values will be treated as ½ *LOQ at all time points.
- MedDRA version 24.0 will be used to code adverse events and medical history, World Health Organization (WHO) drug dictionary version March 2020 or newest will be used for medication coding.

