6.3 SECONDARY EFFICACY ENDPOINTS

6.3.1 DICHOTOMOUS OR BINARY ENDPOINTS

The definition of the dichotomous secondary efficacy endpoints (i.e., responders) are listed in Table 3 below.

Table 3 Definition of Secondary Binary Endpoints

Outcome	Measure	Definition	Analysis Timepoints
Clinical Remission	CDAI	Crohn's disease activity index [CDAI] < 150	Week 12
Endoscopic and clinical improvement	SES-CD and CDAI	Decrease in SES-CD ≥ 50% AND reduction in CDAI ≥ 100 points from Baseline, or CDAI < 150	Week 12
Biomarker and Clinical Composite Improvement	hsCRP and CDAI	Decrease in hsCRP or fecal calprotectin ≥ 50% from Baseline and reduction in	Week 12

		CDAI \geq 100 points from Baseline, or CDAI < 150	
Clinical Response	CDAI	Reduction in CDAI \geq 100 points from Baseline or CDAI < 150	Week 12
PRO-2 remission	Abdominal pain score and Stool frequency	Average daily abdominal pain score \leq 1 point and average daily stool frequency \leq 3 points with abdominal pain and stool frequency no worse than Baseline	Week 12
Normalization of hsCRP	hsCRP	hsCRP < ULN, among subjects whose baseline hsCRP \geq ULN	Baseline, Week 12
Normalization of fecal calprotectin	fecal calprotectin	fecal calprotectin < ULN, among subjects whose baseline fecal calprotectin \geq ULN	Week 12
Anti-drug antibody (ADA) and Neutralizing antibody (Nab)	ADA and Nab	Positive ADA at any time; Positive Nab at any time	Over time

Abbreviations: SES-CD, Simple endoscopy score for Crohn's disease; CDAI, Crohn's disease activity index; hsCRP, High sensitivity C-reactive protein; PRO-2, Two component patient-reported outcome; ADA, Anti-drug antibody; Nab, Neutralizing antibody.

The proportion of clinical remission in FAS will be analyzed according to the method similar to the sensitivity analysis for the primary efficacy endpoint, in the case of missing data in CDAI at Week 12. If the resulting lower limit of 95% confidence interval is greater than 16%, the observed remission rate for the placebo treated patients from multiple prior CD trials ([1], [7], [8], [9], [10]), the null hypothesis for the first secondary endpoint of clinical remission at Week 12 will be rejected at a 1-sided significance level of 0.025.

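### The biomarker-and-clinical composite lets a 50% fall in a marker that was normal at Baseline count as biomarker improvement, and the SAP gives two different denominators for it

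*SAP*

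**What the plan says.** The composite is defined in four places, in two forms.

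- **SAP Section 2, Table 1:** the biomarker part is a "decrease in hsCRP OR fecal calprotectin" of at least 50% from Baseline, in the population "among subjects with at least one elevated biomarker at Baseline, AND reduction in CDAI" of at least 100 points, or CDAI below 150.
- **Protocol 3.2:** the same either-marker rule and the same subject-level restriction, "among subjects with at least one elevated biomarker at Baseline".
- **SAP 6.3.1, Table 3:** "Decrease in hsCRP or fecal calprotectin ≥ 50% from Baseline and reduction in" CDAI. There is no Baseline-elevation condition.
- **Protocol 6.4:** "Biomarker and Clinical Composite Improvement – a decrease in hsCRP or fecal calprotectin" of at least 50%, plus the CDAI reduction. Again there is no elevation condition.

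The normalization rows of SAP Table 3 tie the condition to the marker being judged. For hsCRP the row reads "hsCRP < ULN, among subjects whose baseline hsCRP" is at or above ULN, and the calprotectin row follows the same pattern.

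Two further rules matter. SAP 4.1 takes Baseline as the single last non-missing pre-dose value. It also says "PD/biomarker BLQ concentration values will be treated as" half the LOQ at all time points. SAP 6.5 lists hsCRP and fecal calprotectin as PD markers, so that rule reaches both.

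SAP 6.3.1 reports the secondary endpoints as a point estimate with a 95% CI in the FAS, with missing values counted as non-response. SAP 6.10 confines formal testing to the primary endpoint and clinical remission.

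**The concern.** Induction is open-label and single-arm, and CDAI contains several subject-reported items. The biomarker half of the composite is there to give objective support to the clinical half. It does so only if the marker that improves was abnormal to begin with. As written, variation within the normal range of one marker can satisfy the biomarker half while the elevated marker is unchanged or worse. For a given set of eligible subjects, this can only raise the reported proportion.

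The conflict between Table 1 and Table 3 is a separate fault. One restricts the denominator to subjects with an elevated marker and the other does not, so the same data can yield two results for one secondary endpoint.

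**Working it through.** The plan states no rate, sample size or power for this composite, so there is no figure to reproduce. The check compares the definitions and then sizes the effect under stated assumptions.

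**1. What the definitions allow.** Take a subject with calprotectin above ULN and hsCRP below ULN at Baseline.

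| Source | Eligible? | hsCRP halves, calprotectin does not improve |
|---|---|---|
| SAP Table 1, Protocol 3.2 | yes | biomarker part met |
| SAP Table 3, Protocol 6.4 | yes, no condition | biomarker part met |

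A subject with neither marker elevated is outside Table 1 but inside Table 3. SAP Section 10 does not list dropping the condition as an intended change.

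**2. The half-LOQ rule.** For a quantifiable Baseline B followed by a Week 12 value below LOQ, the scored fall is 1 − 0.5 × LOQ/B.

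- B = LOQ: 1 − 0.5 = 50%
- B = 1.2 × LOQ: 1 − 0.5/1.2 = 58%
- B = 2 × LOQ: 1 − 0.5/2 = 75%

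Every such pair meets the threshold. The rule also works the other way. If Baseline is below LOQ it is set to 0.5 × LOQ, and no later value can be scored below 0.5 × LOQ, so that marker cannot register a 50% fall. The documents give neither the LOQ nor the frequency of such pairs.

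**3. Chance of halving with no true change.** The documents give no assay variability, so within-subject log SD s is assumed. For one Baseline and one Week 12 value, with no selection on Baseline, P = Φ(−ln 2 / (s√2)). This must be corrected, because the marker in question was below ULN at Baseline. Such values are low partly by chance and tend to rise on remeasurement. The last column simulates this with between-subject log SD 0.8 or 1.2 and population mean (log scale) at ULN or at 2 × ULN, keeping only Baseline below ULN.

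| s | No selection | Baseline below ULN |
|---|---|---|
| 0.3 | 5% | 2% to 4% |
| 0.4 | 11% | 4% to 8% |
| 0.5 | 16% | 6% to 11% |
| 0.7 | 24% | 8% to 15% |

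The last column, about 2% to 15% overall, is the relevant one.

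**4. Effect on the composite.** Let c be the probability that the CDAI part is met, e the probability that an elevated marker falls by at least 50%, d the share of eligible subjects with one elevated and one normal marker, and q the chance of a fall in the normal marker. All are assumed and treated as independent.

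- Rate as worded: c × [e + d(1 − e)q]
- Rate if the falling marker must be the elevated one: c × e
- Overstatement: c × d × (1 − e) × q

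Take c from 40% to 60%, e from 30% to 50%, d from 20% to 40%, and q from 2% to 15%:

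- Smallest: 0.40 × 0.20 × 0.50 × 0.02 = 0.0008, about 0.1 percentage points
- Largest: 0.60 × 0.40 × 0.70 × 0.15 = 0.0252, about 2.5 points (20.5% as worded against 18.0%)

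Raising q to 20% gives 0.60 × 0.40 × 0.70 × 0.20 = 0.0336, or 3.4 points, but that q lies above the range in step 3. Even if all 50 subjects were eligible, 2.5 points is 0.0252 × 50 = 1.3 subjects.

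**The case against.** The strongest reply is that little depends on this endpoint. It is descriptive and outside the hierarchy, a responder must still meet the CDAI part, and the likely overstatement is about one subject at most. All of this stands, and it limits the weight of the point.

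A second reply is that accepting either marker is a legitimate design choice, and that marker-specific results appear elsewhere, in the two normalization endpoints and the PD summaries. This stands in part. Those outputs show each marker separately, but not whether the subjects counted as composite responders improved on the marker that was abnormal. Nor do they resolve the two denominators.

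A third reply is that changing a secondary endpoint definition in an open-label trial, when the subject-level wording is also in the protocol, has its own cost. This stands, and the fix allows for it.

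Stronger readings are tempting but not supported:

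- A reader might infer that the composite reduces to CDAI response alone. The sizes above rule that out under the assumed inputs.
- A reader might take 5% to 24% as the chance rate. Those figures ignore that the marker was normal at Baseline.
- A reader might infer from the half-LOQ rule that halving is automatic for normal markers. It is automatic only for a quantifiable Baseline followed by a below-LOQ Week 12 value, and the documents do not say how often that occurs.
- A reader might assume that Table 3 is what will be programmed. The SAP calls it the definition, but Table 1 states the condition and no text ranks the two.

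**Conclusion.** The definition is wrong as written, with modest consequences. The elevation condition applies to the subject and not to the marker that falls, no other section corrects this, and the SAP contradicts itself on the denominator. These conclusions rest on the text alone.

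The size rests on assumptions. A normal-at-Baseline marker falls by 50% or more by chance in about 2% to 15% of cases, and under Table 1 the composite is overstated by roughly 0 to 3 percentage points. Under Table 3's wider denominator the net direction is uncertain, because subjects with no elevated marker also enter. No hypothesis test, power or type I error is affected. The change is worth making because it is cheap and lets the endpoint measure what it is meant to measure.

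**What to change.** 1. In SAP Tables 1 and 3, define biomarker improvement as a fall of at least 50% from Baseline in a biomarker that was at or above ULN at Baseline. If both were elevated, either may qualify.
2. Restore the restriction to subjects with at least one elevated biomarker at Baseline in the Table 3 row, so that both tables share one denominator.
3. List the change in SAP Section 10 as a difference from Protocol 3.2 and 6.4. SAP Section 1 already requires changes made after approval to be documented with their rationale in the clinical study report.
4. Report the either-marker definition, as the plan now has it, as a supplementary tabulation in the same restricted population.

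The cost is a few lines of SAP text and one extra table, with no new data or visits. The reported proportion may fall slightly. A secondary endpoint definition also changes in an open-label trial, and the supplementary tabulation makes the effect of that change visible.

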3 STUDY DESIGN

3.1 SUMMARY OF STUDY DESIGN

This is a multi-center, open-label, proof of concept study designed to assess the safety, tolerability, and preliminary efficacy of PRA023 following 12 weeks of induction therapy in subjects with Crohn’s disease (CD). This study will be conducted under the aegis of a Data Monitoring Committee (DMC) and will commence following the demonstration of an acceptable safety profile of PRA023 at a dose of ≥ 500 mg in the multiple ascending dose study in normal healthy volunteers (Study PR200-101).

The study has 4 periods (Screening, IP, OLE and Follow-Up [FU] Period). Following the Screening Period, approximately 50 eligible subjects with moderately to severely active CD will enter the IP to receive PRA023 1000 mg on Week 0/Day 1, followed by 500 mg on Weeks 2, 6, and 10 via intravenous (IV) administration. Subjects who discontinue from the study will have a follow-up period of 12 weeks after the last dose. A schema for the study is in Figure 1.

Figure 1 Study Design

Q4W=every 4 weeks; R=Randomization.

Response at Week 12 is defined as reduction from Baseline in CDAI of ≥ 100 points, or CDAI < 150 . Non-responders at Week 12 should discontinue from study drug treatment.

Subjects who complete the 12-week IP and have responded will have the option to enter OLE, where they will be randomized to either 250 mg IV Q4W or 100 mg IV Q4W until Week 50. Subjects will continue in OLE until they progress, withdraw from the study, study termination, or Week 50.

The study may be amended by the Sponsor to extend the OLE period beyond 50 weeks based on emerging safety data.

For additional details, please see the Schedule of Assessments are described in Appendix G.

3.2 DETERMINATION OF SAMPLE SIZE

The study is planned to enroll approximately 50 subjects. The sample size will enable a statistical power of 80%, at 1-sided significance level of 0.025, to test against the null hypothesis of endoscopic improvement rate of 12%, assuming the endoscopic improvement rate for PRA023 is 27%.

The null hypothesis of an endoscopic improvement (decrease in SES-CD $\geq 50\%$) rate of 12% is based on a meta-analysis estimate of the upper limit of 95% CI of the observed placebo rate (95% CI) of 9.5% (7.1, 11.9) from multiple modern-era CD clinical trials with centrally read endoscopy and similar eligibility criteria. [1]

3.3 RANDOMIZATION

3.3.1 RANDOMIZATION NUMBERS

This is an open-label study where all subjects will receive PRA023. Eligible subjects will be assigned a subject number by the IRT system at Week 0/Day 1 upon confirmation of study eligibility as a means to track the number of eligible subjects enrolled in the study. Subjects who are randomized in OLE will retain their original subject numbers.

